5.1.12.7 Ocular abnormalities

In the event of suspected clinically significant findings (e.g., macular edema or active uveitis), an unscheduled OCT examination should be performed. In the case of macular edema, confirmed by the local ophthalmologist, the subject must be permanently discontinued from study treatment and will be managed and followed up until resolution. Any clinically relevant finding meeting the definition of an AE will be recorded accordingly in the eCRF.

Subjects with active uveitis but without macular edema may continue on the study treatment but will require additional ophthalmologic assessments as detailed below:

5.1.12.7.1 Guidance for monitoring and management of subjects with uveitis

If active uveitis (ocular pain, floaters, blurred vision, increased intraocular pressure) is suspected at EOT or FU1 visit in the core study, or during a scheduled ophthalmological assessment, or at an unscheduled assessment due to ophthalmological symptoms in the extension study, fluorescence angiography (FA) should be performed (unless contra-indicated according to the ophthalmologist) in addition to the scheduled ophthalmological assessment in order to characterize the uveitis. Subjects with suspicion of uveitis occurring during the study treatment but outside scheduled ophthalmological assessment should have a full ophthalmological assessment performed together with FA (unless contra-indicated) and OCT as soon as possible. If active

15 March 2022, page 82/216

EudraCT 2016-004719-10 EDMS-ERI-207656619

Confidential

uveitis can be confirmed and macular edema can be ruled out, the subject may continue in the study without interrupting the study treatment. Such subjects will need to be controlled by the ophthalmologist 1 week, 2 weeks, and 4 weeks after the diagnosis of uveitis has been confirmed, and then every 4 weeks throughout the study or until the condition has resolved. These ophthalmological exams should include full ophthalmological assessment (ophthalmological symptoms, assessment of best corrected visual acuity (Early Treatment Diabetic Retinopathy Study [ETDRS] charts), measurement of tonometry (Goldmann applanation tonometry is recommended, slitlamp examination of the anterior segment, and dilated indirect funduscopy), as well as OCT. FA may be repeated at the ophthalmologist's discretion. The ophthalmologist will decide what treatment should be given to the subject. If the subject needs to be treated by immunosuppressants prohibited by the protocol, the study treatment must be discontinued. If uveitis is progressing in spite of treatment, the investigator may consider interrupting or permanently discontinuing the study treatment.

5.2 Concomitant therapy

A therapy that is concomitant to study-treatment is any treatment that is either ongoing at the start of study treatment or is initiated during the study treatment period, or up to 30 days after the end of study treatment. All study treatment concomitant therapies will be recorded on the Concomitant Medications page of the eCRF. In addition, all medication taken by the subject at EOS of the core study, i.e., all medication ongoing or started at this time, will be recorded on the Concomitant Medications page of the eCRF.

5.2.1 Recommended concomitant therapy

Treatment of relapses:

- If a relapse requires treatment with corticosteroids, methylprednisolone 1 g i.v. daily for 3 to 5 days is recommended. Treatment with other corticosteroids, another dose, other routes of administration, or adrenocorticotropic hormone (ACTH) is not recommended unless deemed absolutely necessary, and must be documented in the subject charts by the investigator. Oral taper with corticosteroids is not permitted.
- Treatment of relapses with plasma exchange (i.e., plasmapheresis, cytapheresis) is prohibited.

5.2.2 Allowed concomitant therapy

- Administration of i.v. atropine in the event of symptomatic bradycardia;
- Short-acting \(\beta 2\)-agonists for respiratory symptoms and/or reduced pulmonary function during study treatment;
- QT-prolonging drugs with known risk of Torsades de Pointes should be used with caution as ponesimod may potentially enhance their effect on QT interval [guidance is provided in Appendix 2];

15 March 2022, page 83/216

Confidential

EudraCT 2016-004719-10 EDMS-ERI-207656619

- Glatiramer acetate and INF β-1a are allowed only during ponesimod interruptions for planned pregnancy. These treatments may be started 7 days after ponesimod cessation and must be stopped 7 days before ponesimod re-initiation;
- Other treatments considered necessary for the subject's wellbeing and not categorized as prohibited concomitant medications.
- Vaccination with non-live vaccines is allowed while on study treatment if the vaccination is advised by the primary investigator / treating neurologist, based on her/his clinical assessment of the risk/benefit for the individual patient, and if supported by guidelines for vaccination relevant to this patient population, as applicable.

5.2.3 Forbidden study-treatment-concomitant therapy

- Systemic corticosteroids and ACTH, except for the treatment of MS relapses [see Section 5.2.1] and for short-term treatment (up to 2 weeks per treatment cycle with at least 8 weeks' interval between treatment cycles and no more than 4 weeks per year of the study duration on average) with low dose of corticosteroid (up to 10 mg of prednisone equivalent daily) or inhaled corticosteroids for pulmonary conditions;
- Disease-modifying drugs for MS other than prescribed as per protocol (except glatiramer acetate or INF β-1a during ponesimod interruptions for planned pregnancy as described under "Allowed").
- Immunosuppressive treatment (e.g., cladribine, lymphocyte-depleting biological agents such as rituximab or ocrelizumab, mitoxantrone, or other systemic immunosuppressive treatments such as azathioprine, cyclophosphamide, cyclosporine or methotrexate);
- i.v. immunoglobulin (except in women who have interrupted study treatment for pregnancy; for these women i.v. immunoglobulin will be allowed after 30 days from interruption of the study treatment);
- Plasmapheresis, cytapheresis, or total lymphoid irradiation;
- Vaccination with live vaccines, except if performed during a temporary treatment interruption
 period. In this case it must be performed not earlier than 1 week after last dose of study
 treatment, and treatment can be re-initiated only after at least 4 weeks from completion of
 vaccination;
- β-blockers, diltiazem, verapamil, digoxin, digitoxin or any other anti-arrhythmic or HR lowering systemic therapy (a non-exhaustive list of drugs provided in Appendix 3) during the up-titration period (i.e., from Day 1 until Day 14 included, and during the first 14 days after re-initiation of study treatment). Treatment with any of these therapies is also not recommended during the maintenance treatment period (from Day 15 until EOT) and should be considered with caution if an alternative medication cannot be used;

Confidential

EudraCT 2016-004719-10 EDMS-ERI-207656619

Any other investigational drug;

15 March 2022, page 84/216

• Any investigational therapeutic procedure for MS (e.g., stent placement or angioplasty for chronic cerebrospinal venous insufficiency, stem-cell transplantation).

Commercially available ponesimod may be initiated on the day following last intake of study treatment. The start date of commercially available ponesimod must be recorded on the Concomitant Medication page of the eCRF.

In the event that a subject takes any of these forbidden medications, the investigator must contact the sponsor to discuss further FU actions, including stopping/interrupting study treatment as appropriate.

6 STUDY ENDPOINTS

Endpoints for the main part of this study are summarized below.

6.1 Efficacy endpoints

In order to monitor disease activity with long-term treatment with ponesimod, and to investigate the effect of switching from teriflunomide to ponesimod, the main analysis of efficacy will focus on the Combined Analysis Period, i.e., including data from both the core and extension studies. In addition, specific efficacy endpoints will also be analysed over the Extension Analysis Period, i.e., only including data from the extension study. Analysis over the Combined Analysis Period will use the core study baseline as a reference, while analysis over the Extension Analysis Period will use the extension study baseline as a reference. Baseline definitions for efficacy endpoints are provided in Section 11.1.3.

The tables below detail which endpoints will be analyzed for the Extension Analysis Period, and which for the Combined Analysis Period. See Section 11.1 for further details regarding the analysis strategy.

6.1.1 Main clinical endpoints

The main clinical endpoints are those relating to disease activity (relapses, disability accumulation, and composite of the latter including MRI).

15 March 2022, page 85/216

Confidential

Table 6Main clinical endpoints

Endpoints	Combined Analysis Period	Extension Analysis Period
 ARR (based on the number of confirmed relapses* per subject-year) 	Y	Y
 Time from core study randomization to first confirmed relapse* 	Y	N
 Time from core baseline to 12-week CDA 	Y	N
 Absence of relapses* 	Y	Y
• Time from core baseline to 24-week CDA	Y	N
 Change from baseline in EDSS at all assessments 	Y	Y
• NEDA status at EOS according to NEDA 3 (defined by the absence of confirmed relapse, Gd+ T1 lesions, new or enlarging T2 lesions and 12-week CDA)	Y	N
• NEDA status at EOS according to NEDA 4 (defined by the absence of confirmed relapse, Gd+ T1 lesions, new or enlarging T2 lesions, 12-week CDA, and annual brain volume change ≥-0.4% from baseline to all assessments)	Y	N

*Definition of relapse

- A relapse is defined as new, worsening or recurrent neurological symptoms that occur at least 30 days after the onset of a preceding relapse, and that last at least 24 hours, in the absence of fever or infection.
- The new, worsening or recurrent neurological symptoms are to be evaluated by the treating neurologist and, if all the elements of the above definition have been verified, and in the absence of another, better explanation of the subject's symptoms, the event is considered as a relapse [see Section 7.4.2]. The onset date of the relapse corresponds to the onset date of the symptoms.
- A relapse will be confirmed by the treating neurologist only when the subjects' symptoms are accompanied by an increase in EDSS/FS scores, which is consistent with the subject's symptoms, from a previous clinically stable EDSS/FS assessment (i.e., performed at least 30 days after the onset of any previous relapse), obtained by the efficacy assessor and consistent with the following:
 - An increase of at least half a step (0.5 points; unless EDSS = 0, then an increase of at least 1.0 points is required) or
 - An increase of at least 1.0 point in at least two FS scores, or
 - An increase of at least 2.0 points in at least one FS score (excluding bladder/bowel and cerebral).

ARR = annualized relapse rate; CDA = confirmed disability accumulation; EDSS = Expanded Disability Status Scale; EOS = End-of-Study; FS = functional system; NEDA = no evidence of disease activity.

Confidential

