3 OVERALL STUDY DESIGN AND PLAN

3.1 Study design

This study is a prospective, multicenter, open-label, non-comparative, long-term extension of the Phase 3 confirmatory core study.

Subjects who have completed the 108-week treatment period in the core study will be enrolled into one group treated with ponesimod 20 mg o.d. Based on anticipated discontinuation rates in the core study, approximately 800 subjects are expected to enter the extension study.

The study will be conducted in approximately 160 sites in 28 countries.

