3.2.3 Treatment period

The treatment period starts with the first dose of study treatment, which defines Day 1 of the extension study. All post-dose assessments of Visit 1 will be conducted during the treatment period.

Ideally, all assessments and procedures of Visit 1, including first study treatment dosing and post-dose cardiac monitoring, should occur on the same day as the core study FU1 or abbreviated FU2 (whichever applies). In all cases, all assessments and procedures of Visit 1 must be completed (i.e., study treatment start) no longer than 7 days after signing of the informed consent (start of Visit 1).

The time from last dose of study treatment in the OPTIMUM study to the first dose of ponesimod in this study will last at least 14 days, but can last up to 44 days. The investigator should make every effort to minimize the duration of the treatment interruption between EOT of the core study and Day 1 of the extension study. Ideally, the treatment interruption should not last longer than 15 days.

The treatment period consists of 240 weeks of treatment with ponesimod including a 14-day gradual up-titration beginning on Day 1, followed by daily treatment with 20 mg ponesimod.

15 March 2022, page 51/216

Confidential

EudraCT 2016-004719-10 EDMS-ERI-207656619

Treatment will stop before 240 weeks if ponesimod becomes commercially available for the treatment of multiple sclerosis in the subject's country.

The visits during the treatment period will consist of an enrollment visit; three visits at 2 (i.e., 15 days), 4, and 12 weeks after enrollment; and visits every 12 weeks thereafter until the EOT.

The treatment period may include a study treatment interruption period of variable duration [see Section 5.1.12]. The permitted maximum duration of the study treatment interruption is 81 weeks for planned pregnancies and 12 weeks for other reasons (if exceeded, then the subject will be prematurely discontinued from the study). During the treatment interruption the subject will follow the planned visit schedule off-treatment with the corresponding assessments with exceptions of assessments that are contra-indicated due to the subject's condition (e.g., in the event of pregnancy, scheduled MRI assessments will not be performed).

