11.1.4.2 Combined analysis period

For efficacy this period includes all available data from randomization in the core study up to the extension EOS date for subjects entering the extension, or up to the core EOS date for subjects not entering the extension. For safety this period includes all available data from the date of first treatment administration up to the last treatment date + 15 days in the extension study for subjects entering the extension, or up to the last treatment date + 15 days in the core study for subjects not entering the extension.

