11.2.2 Full Analysis Set

Following the intention-to-treat (ITT) principle, the Full Analysis Set (FAS) includes all subjects randomized in the core study. Subjects will be evaluated according to the treatment they have been randomized to in the core study, which may be different from the treatment they have received.

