11.2.6 Usage of the analysis sets

The EXTS will be used for efficacy and safety analyses of the Extension Analysis Period. The FAS and EXTS will be used for efficacy analyses of the Combined Analysis Period. The SAF will be used for the safety analysis of the Combined Analysis Period in an as-treated approach.

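### NEDA-3 and NEDA-4 are fixed as status at each subject's own end of study, with no common time point, although follow-up runs from under 2 to about 6.9 years

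*Protocol*

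**What the plan says.** Protocol Section 6.1.1, Table 6, lists "NEDA status at EOS according to NEDA 3" and a matching NEDA 4 row among the main clinical endpoints. Both are defined by absence of confirmed relapse, MRI lesion activity and 12-week confirmed disability accumulation (CDA); NEDA 4 adds a brain-volume criterion. Both are marked for the Combined Analysis Period only. A further row, "Absence of relapses", names no time point and is marked for both the Combined and the Extension Analysis Periods.

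For efficacy, Section 11.1.4.2 runs the Combined Analysis Period from core randomization "up to the extension EOS date for subjects entering the extension, or up to the core EOS date for subjects not entering the extension". The extension EOS is not a common date either. Section 3.2.3 says "Treatment will stop before 240 weeks if ponesimod becomes commercially available for the treatment of multiple sclerosis" in the subject's country.

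The Full Analysis Set (FAS) "includes all subjects randomized in the core study" (Section 11.2.2). Section 11.2.6 adds the Extension Set (EXTS): "The FAS and EXTS will be used for efficacy analyses of the Combined Analysis Period". Section 11.6 expects about 800 of the 1100 planned core subjects to enter the extension.

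Other event endpoints allow for unequal follow-up. The annualized relapse rate (ARR) uses a log-time offset (Sections 11.4.2.1 and 11.4.2.3). Time to first relapse and time to CDA are censored (Sections 11.3.1.2 and 11.3.1.3) and analysed by Kaplan-Meier, with relapse tabulated every 12 weeks (Sections 11.4.3 and 11.4.4). No such analysis is described for NEDA.

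**The concern.** Remaining free of all events is easier over two years than over seven. A yes/no status taken at each subject's own last date therefore reflects length of observation as well as disease control. Length of observation here depends on core drop-out, on the choice to enter the extension, on withdrawal during the extension and on the launch date in each country.

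Two things are at stake. First, the pooled proportion is not the share free of disease activity at any stated time, so it cannot support a statement about long-term control. Second, Section 11.1.1 sets out to compare early with delayed ponesimod by core arm. If the arms differ in early leaving or in extension entry, their NEDA proportions differ even when disease activity is equal. Launch-driven exits mainly shift the level; differential drop-out or entry is what would bias the comparison.

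**Working it through.** The protocol gives no expected NEDA proportion, so there is no plan figure to reproduce. The check covers the range of follow-up and what it does to the relapse component.

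**Follow-up.** Inputs: 108 core weeks (Section 3.1), up to 240 extension weeks and a 14 to 44 day gap between studies (Section 3.2.3), EOS 30 to 44 days after stopping (Section 8.4.1).
- Treatment alone: 108 + 240 = 348 weeks = 6.67 years.
- To extension EOS: 348 × 7 + 14 + 30 = 2480 days (week 354, 6.79 years), up to 348 × 7 + 44 + 44 = 2524 days (week 361, 6.91 years).
- Core completer who does not enter: at least 108 × 7 / 365.25 = 2.07 years. Core drop-outs have less.
- Share without extension follow-up: 300/1100 = 27%.

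**Relapse-free probability.** P(t) = exp(−rt) for dispersion k = 0, and (1 + krt)^(−1/k) otherwise. The rates come from Section 1.3.2.3: 0.202 (core ponesimod ARR) and about 0.15 (long-term phase 2 estimate). No dispersion is given, so k = 0 to 1 is an assumption.

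| ARR | k | 1.0 y | 2.1 y | 6.8 y |
|---|---|---|---|---|
| 0.202 | 0 | 0.817 | 0.654 | 0.253 |
| 0.202 | 1 | 0.832 | 0.702 | 0.421 |
| 0.15 | 0 | 0.861 | 0.730 | 0.361 |
| 0.15 | 1 | 0.870 | 0.760 | 0.495 |

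**Crude share if event-free leavers keep their status.** Assume 27.3% leave at 1.0 or 2.1 years and the rest are followed to 6.8 years. Crude share = 0.273 × P(leave) + 0.727 × P(6.8).
- ARR 0.202, k = 0, leaving at 1.0 y: 0.273 × 0.817 + 0.727 × 0.253 = 0.407, against 0.253 (about 15 points too high).
- ARR 0.15, k = 1, leaving at 2.1 y: 0.273 × 0.760 + 0.727 × 0.495 = 0.567, against 0.495 (about 7 points too high).
- The other combinations, including k = 0.5, lie between these.

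**Arm difference with equal true rates.** Assume 22% of one arm and 32% of the other leave at 1 year. The spurious difference is 0.10 × [P(1.0) − P(6.8)]: 0.10 × (0.817 − 0.253) = 5.6 points at ARR 0.202, k = 0, and 0.10 × (0.870 − 0.495) = 3.7 points at ARR 0.15, k = 1.

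**Other rules for event-free leavers** (ARR 0.202, k = 0, leaving at 1.0 y, true value 0.253).
- All leavers counted as failures: 0.727 × 0.253 = 0.184.
- Event-free leavers set to missing, leavers with an event kept: 0.184 / [0.727 + 0.273 × (1 − 0.817)] = 0.184 / 0.777 = 0.237.

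Neither rule returns 0.253, and the three rules together span 18% to 41%.

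**Why no NEDA figure is given.** For a 5-point difference in extension entry, the Poisson shift is 5 × [exp(−2.07r) − exp(−6.67r)] points. That is 5 × (0.658 − 0.260) = 2.0 at r = 0.202, but only 0.6 at r = 1. The shift does not simply grow as event types are added.

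**The case against.** The best reply is that the protocol never says how an event-free early leaver is classified. NEDA is not among the variables derived in Section 11.3.1, Sections 11.3.2 and 11.4.7 leave the other efficacy variables to the statistical analysis plan, and Section 11 bases categorical percentages on non-missing observations. That plan could set such subjects to missing or to failure. This stands as far as classification goes: a reader might infer that early leavers count as successes, but no text says so. The inference also fits only event-free leavers, since a leaver with an earlier event remains a failure. It does not rescue the endpoint, because a missing-data rule added to a status at EOS still supplies no common horizon.

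Three further readings go too far.
- A reader might take all three Table 6 rows as tied to EOS. Only the NEDA rows are.
- A reader might conclude that relapse freedom has no analysis at common times. The Kaplan-Meier analysis in Section 11.4.3 already gives it every 12 weeks for the Combined Analysis Period. The gap is the Extension Analysis Period, where Table 6 does not list time to relapse.
- A reader might expect a larger distortion for NEDA because it has more event types. The last calculation above shows that the shift can shrink at high event rates.

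The EXTS analysis also helps, since it removes core drop-outs and non-entrants. It leaves launch-driven exits and early withdrawals from the extension. Section 11.4.2.4 acknowledges bias from missing extension data and promises worst, best and most plausible case imputation, but for ARR. Finally, the study is exploratory with no hypotheses (Section 11.4.1), and the synopsis does not list NEDA among its main endpoints. This limits the weight of the point; it does not make a proportion over mixed horizons interpretable.

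**Conclusion.** The point holds for NEDA-3 and NEDA-4. The protocol fixes them as absence of events at a subject-specific EOS, over follow-up from under 2 years (FAS) to about 6.9 years. They are the only composite disease-activity endpoints in Table 6, and they have no analysis that allows for unequal follow-up.

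On the literal wording, the relapse component alone would be overstated by about 7 to 15 points at 6.8 years. An assumed 10-point difference in early leaving would create a difference of about 4 to 6 points between arms with equal disease activity. These figures assume a constant rate of 0.15 to 0.202 per year, dispersion of 0 to 1, and leaving at the times shown. They illustrate the mechanism and do not predict NEDA results.

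For absence of relapses the point is smaller: the better analysis is already planned for the Combined Analysis Period and is lacking only for the Extension Analysis Period. Since no decision rests on these endpoints, this is a worthwhile, inexpensive improvement and not a threat to the study.

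**What to change.** In Table 6, replace NEDA status at EOS with time from core randomization to first loss of NEDA-3 and, separately, of NEDA-4.
- Date each loss from the component that caused it: relapse onset, start of the 12-week CDA, or the scan date for lesions and brain volume.
- Censor event-free subjects at their last complete assessment of all components. Section 8.4.1 lists no MRI at the EOS visit, so this will usually be an earlier date than EOS.
- Report Kaplan-Meier proportions by core arm at fixed weeks aligned to the MRI schedule, for the FAS and the EXTS. Core Week 108 is one. Extension Weeks 48, 96, 144, 192 and 240 fall about 110 to 114 weeks later on the core clock (108 weeks plus the 14 to 44 day gap).

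For absence of relapses, take the Combined Analysis Period proportion from the analysis in Section 11.4.3, and add the same analysis from first extension dose for the Extension Analysis Period.

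The cost is the Table 6 wording and one derivation, from data already collected. MRI loss is dated only to the scan, so the curves will step at scan times. The proportions may look less favourable than a crude status. Censoring removes the effect of unequal follow-up but not of withdrawal related to disease activity; the worst, best and most plausible cases promised for ARR in Section 11.4.2.4 could be carried over to cover that.
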